(i.e., weight loss and reductions in blood pressure without hypoglycemia) for patients with DM2 that may be ideally suited for post bariatric patients (10,11). *Thus, the purpose of this proposal is to evaluate the efficacy of canagliflozin in the post-operative management of DM2. We hypothesize that glucose lowering strategies that act independently of insulin and facilitate weight loss, will lead to better glycemic control and produce more favorable cardiometabolic changes than standard of care approach for post bariatric patients with persistent type 2 diabetes.* Therefore, the specific aims are:

1. Determine the clinical efficacy of canagliflozin vs. placebo in patients with type 2 diabetes post-bariatric surgery.

To test the clinical efficacy of canagliflozin in post bariatric patients (i.e., adjustable gastric banding [AB], Roux-en-y gastric bypass [RYGB] and sleeve gastrectomy [SG]) with type 2 diabetes, we will perform a randomized clinical trial of post bariatric surgery (>1 year) patients (N=36) and assign them into either a 6 month intervention of a) canagliflozin monotherapy (300mg qd) (N= 24) or b) placebo (N = 12). Including AB, RYGB, and SG subjects would give a more comprehensive understanding of the effects of canagliflozin, in the post-operative setting, given that they are the most common metabolic surgeries. The primary outcome measure is the change in Hba1c from randomization until 6 months in the medication group, relative to placebo. Secondary measures include the percentage of subjects who achieve glycemic control at 6-months (i.e., Hba1c <6.5%), fasting glucose, change in body weight, lipid, blood pressure control and symptomatic hypoglycemia episodes (per AE reporting).

2. Determine whether the cardiometabolic benefits of canagliflozin in post-bariatric individuals with diabetes is related to improvements in weight loss and adipokine (ie. adiponectin) levels.

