Our bariatric surgical program is a Center for Excellence and a high volume provider of gastric bypass procedures for patients with medical indications with follow up care provided by endocrinologists and a multidisciplinary obesity team. This program provides an ideal environment in which to pursue novel and innovative approaches that couples medical care delivery with research that is both clinically significant and scientifically meaningful using a novel and innovative approach.

PRELIMINARY DATA:

1. Diabetes remission/non-remission rates following bariatric surgery from Cleveland Clinic observational study (*Annals of Surgery*, 6/2013 epub. *Brethauer S et al.*)

N= 217 consecutive subjects with type 2 diabetes of median 6yr duration, Hba1c of 7.5%, BMI of 50 kg/m², age 49 yrs. N= 162 following gastric bypass with complete diabetes remission (HbA1c <6%) of 31%; diabetes non-remission of 69% and diabetes recurrence rate of 17% during 6 year median follow up. Predictors of remission: weight loss (P 0.006), short diabetes duration (P =<0.001) and bypass vs. banding procedure (P = 0.02).

2. Diabetes remission/non-remission rates and weight regain in on-going STAMPEDE trial follow up at 24 months:

Subjects with type 2 diabetes in STAMPEDE trial N= 150 randomized to medical therapy (N= 50) vs. Roux-n-Y gastric bypass (n = 50) or SG (N = 50) ; baseline age 48 yrs., diabetes duration 8 years, BMI 36 kg/m2, HbA1c of 9%.

	Gastric Bypass	Sleeve Gastrectomy
Rate of HbA1c > 6.5%-12 months	16/48 (33.3%)	22/48 (45%)
Rate of HbA1c > 6.5%-24 months	14/36 (38.9%)	14/36 (38.9%)
Rate of HbA1c > 6.5%-36 months	12/23 (52.2%)	12/23(52%)
Weight regain-24 months	30/36 (83%)	32/38 (84%)

Weight increase from nadir 24 months (Kg)	5 ± 3.9	4.9 ± 4
Weight increase from nadir 36 months (Kg)	7.6 ± 5	10.3 ± 11

Diabetes non-remission defined by HbA1c \geq 6.5% increased following both surgery types (especially the SG procedure) at 24 and 36 months follow up along with weight regain from nadir weight following both procedures. These data are accumulating and unpublished since the trial is on-going for collection of follow up data. Initial primary endpoint of diabetes remission rate (HbA1c \leq 6% of 42% after gastric bypass) reported in *NEJM, April 2012 (Schauer, Kashyap, Wolski et al.)*.

3. Metabolic Determinants of HbA1c \leq 6.5% at 24 months in subset (N= 60) of medical and surgical patients enrolled in STAMPEDE trial:

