A multivariate logistic model of metabolic parameters that associated with HbA1c \leq 6.5% at 24 months in the substudy cohort of 54 subjects that underwent medical, RYGB, and SG intervention arms combined demonstrated that the fold increase in the oral disposition index (β cell function) was associated with an increased OR of 1.67, and the increase in abdominal fat was associated with a lower OR of 0.878 to achieve glycemic control at 24 months. (*Kashyap et al. Diabetes Care; Feb 24, 2013 epub*). This suggests that improved β cell function and reduction of abdominal fat are key metabolic determinants of remission vs. non-remission status in medical and surgical subjects.

4. Poor Improvement in Adiponectin Levels and Inadequate Fat/Weight Loss Depict Surgical Non-remission at 24 months in STAMPEDE:

The 37 (BMI: 36 ± 3 kg/m², Age: 48 ± 9 y, HbA1c: $9.7 \pm 2\%$) DM2 post-bariatric (RYGB and SG) surgery subjects who underwent RYGB and SG were analyzed based on remission vs. non-remission status defined by HbA1c of $< 6.5\%$ or $> 6.5\%$ and/or hypoglycemic medications. Bariatric surgery-induced 45% and 38% DM2 remission rates at 12 and 24m, respectively, with RYGB yielding higher remission rates than SG at 24m ($P < 0.05$). (Data submitted to ADA 2014 Scientific Sessions). As shown in the table, surgical remitters had greater weight loss, total body fat loss, rises in adiponectin levels and higher levels of GLP-1 stimulation with meal intake.

Variables at 24 months	Remission (HbA1c $< 6.5\%$)	Non-remission (HbA1c $> 6.5\%$)	P-value
BMI (kg/m ²) change	-9.97 (-10.6, -7.9)	-6.8 (-9, -6.06)	0.03
Body fat % change	-11.1 (-14.6, -7.8)	-7.4 (-10, -4.6)	0.04
Adiponectin ng/ml change	2.9 (1.7, 4.4)	-0.1 (-2.2, 0.9)	0.003
Truncal fat % change	-13.8 (-21.5, -10)	-10 (-13, -5.7)	0.04
Change in Disposition Index	0.31	0.06	< 0.001

Baseline adiponectin predicted lower HbA1c at 12 and 24m ($R=0.34$, $P=0.04$ and $R=0.33$, $P=0.04$). Elevated adiponectin correlated with enhanced β -cell function at 12 ($R=0.33$, $P=0.04$) and 24m ($R=0.47$, $P < 0.01$) as well as weight loss at 24m ($R=-0.32$, $P=0.05$). Thus, poor fat loss and blunted rises in adiponectin depict DM2 non-remission 2 years after bariatric surgery.

5. Observational data on the use of generic phentermine and topiramate on residual diabetes in

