Comparisons of the primary endpoint, change in HbA1c levels from randomization, between canagliflozin and placebo groups will be performed using analysis of covariance models. Since the correlation between baseline levels of HbA1c and change in the measure at 6 months is not presently well known, power calculations are based on use of two-sample t-tests, which assume similarity of the two randomized groups on HbA1c at baseline. Enrollment of 36 patients is planned. Assuming use of a two-sided t-tests with a significance level of 0.05, and that variability in HbA1c change at 6 months is similar to that seen at 1 year in Cefalu et al. (2013) [SD=0.9%], there will be 80% power to detect mean differences of 1.0% in HbA1c change between groups with enrollment of 22 patients in the canagliflozin group and 11 in the placebo group. Power calculations were performed using SAS software (Version 9.4; Cary, NC). If we assume dropout of 10%, and enroll 24 patients in the canagliflozin group and 12 in the placebo group, this should allow for adequate power despite the expected loss to follow-up. Since analysis of covariance models will provide increased

power relative to t-tests in the presence of positive correlation (Borm et al, 2007), the effect size that can be detected is conservatively large.

Nutritional assessment for vitamin/mineral deficiency will be performed per clinical care guidelines(46) at the screening visit. Subjects will be asked to take nutritional supplements (i.e. vitamins and minerals) per current clinical guidelines for post-bariatric patients. Stable doses of supplements will be established for at least 2 weeks prior to randomization. Thirty-six subjects with recurrent diabetes that are naïve to hypoglycemic agents with HbA1c greater than or equal to 6.5% and less than 11% will be randomly assigned to a six month course of a) canagliflozin 100mg for 2 weeks titrated up to 300 mg daily (N = 24) vs. placebo (n= 12) at the randomization. Patients taking an anti-diabetic medication will be asked to washout for 8 weeks prior to the randomization visit. At randomization, biochemical assessment of glycemic parameters (fasting glucose, HbA1c), lipid panel, complete metabolic panel, uric acid, leptin, total and HMW adiponectin, C-reactive protein and urine for albumin/creatinine ratio will be performed. DXA scan will be performed for body fat composition.

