The primary analysis will be performed using a modified intent to treat analysis which includes all patients receiving at least one dose of the drug they were assigned. A secondary, per-protocol analysis may also be performed using those demonstrating compliance to their assigned treatment throughout the study. All endpoints will be evaluated using a significance level of 0.05, and no correction for multiple testing is planned.

To evaluate changes in HbA1c and other continuous endpoints at 6 months, analysis of covariance models will be fit. In these models, change from baseline will be the outcome, group membership will be the predictor of interest, and baseline level of the outcome will be a covariate. If distributional assumptions of the model are not met, transformation of the outcome measure will be considered to improve model fit, as will the use of alternative rank-based approaches. Estimated changes and differences in the changes at 6 months between groups will be presented with 95% confidence intervals. Categorical factors will be presented using frequencies and percentages, and comparisons of these measures between groups will be performed using Pearson chi-square tests or Fisher exact tests, as appropriate. Continuous patient characteristics will be summarized using means and standard deviations or medians and quartiles, depending on their distribution.

Inclusion Criteria:

1. Post-AB, RYGB, and SG patients who underwent surgery >1 and <15 years ago, in the Cleveland surrounding area
2. 20-75 years of age

3. DM2 diagnosis (history, medication usage, biochemical criteria) prior to and after surgery; after surgery, defined by a single HbA1c of greater or equal to 6.5% at consent and screening.

4. Metformin patients must have an HbA1c greater than or equal to 6.5% but less than or equal to 11% at randomization; for diet controlled patients (i.e. not on any T2D medication), HbA1c must be greater than or equal to 6.5% at randomization.

5. Patient reporting of improvement in T2D status or objective improvements in T2D status at any time post-surgery.

6. eGFR \geq 60mL/min prior to randomization

7. Has the ability and willingness to provide informed consent.

8. Is able to understand the options and to comply with the requirements of each program.

9. Female subject agrees to have a serum pregnancy test at screening. A negative serum pregnancy test result is required prior to randomization.

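### Surgery type, which the protocol names as a predictor of diabetes remission, enters neither the stated allocation nor the ANCOVA, leaving avoidable chance imbalance in a 36-patient trial

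*Combined protocol and SAP*

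**What the plan says.** Aim 1 (Purpose of Protocol) enrols patients after adjustable banding (AB), gastric bypass (RYGB) or sleeve gastrectomy (SG): "Including AB, RYGB, and SG subjects would give a more comprehensive understanding of the effects of canagliflozin, in the post-operative setting". The sentence goes on to give as its reason that these operations are the ones most often performed.

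Surgery type is presented as prognostic in four places:
- The opening paragraph of Purpose of Protocol lists it among the determinants of durable remission.
- The background section on re-emergence of diabetes lists restrictive versus bypass surgery as a possible factor in non-remission.
- Preliminary Data item 1 reports bypass versus banding as a predictor of remission (P = 0.02).
- Preliminary Data item 4 reports remission "with RYGB yielding higher remission rates than SG at 24m" (P < 0.05, 37 patients).

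The table in Preliminary Data item 2 is less clear. Rates of HbA1c above 6.5% after bypass and sleeve are 16/48 and 22/48 at 12 months, but 14/36 in both at 24 months and 12/23 in both at 36 months.

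Allocation is described only as random. Sample Size Considerations plans to "enroll 24 patients in the canagliflozin group and 12 in the placebo group", with no stratification factor or blocking stated. In Statistical Methods, the model for continuous endpoints is change from baseline, where "group membership will be the predictor of interest, and baseline level of the outcome will be a covariate". No other covariate and no estimate by procedure is planned.

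**The concern.** Surgery type is known for every patient at eligibility, before randomization. If it predicts the outcome, leaving it out of both the allocation and the model has two costs. The arms may by chance differ in procedure mix, which makes a small trial harder to interpret and invites a post hoc decision about adjustment. The variance that surgery type explains also stays in the error term. With 12 patients on placebo, a few patients make a large percentage difference. The comparisons affected are HbA1c change (primary), body weight (secondary) and body fat (exploratory).

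**Working it through.** **Inputs.** From Sample Size Considerations: 24 and 12 randomized, 22 and 11 behind the power statement, SD of HbA1c change 0.9, difference 1.0, two-sided 0.05. Assumed, because the documents do not give them: the number of bypass patients among the 36 (K), and the difference in mean HbA1c change between bypass and non-bypass patients (g).

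**1. The plan's own figure.** The plan says "there will be 80% power to detect mean differences of 1.0% in HbA1c change between groups" at 22 and 11. The standard error is 0.9 × √(1/22 + 1/11) = 0.332, so the noncentrality is 1.0/0.332 = 3.01. On 31 degrees of freedom the power is 83.0%. At 20 and 10 it is 79.1%, so 22 and 11 is the smallest exact 2:1 design reaching 80%. The stated size is sound.

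**2. Chance imbalance if allocation is unstratified.** With a fixed 24:12 split, the number x of bypass patients on placebo is hypergeometric (36 patients, K bypass, 12 drawn). The gap in bypass share is x/12 − (K − x)/24. For K = 18 this equals (3x − 18)/24, which is at least 0.20 in size when x ≤ 4 or x ≥ 8.

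| K (bypass of 36) | P(gap ≥ 20 points) | P(gap ≥ 30 points) |
|---|---|---|
| 12 | 26% | 5.8% |
| 18 | 29% | 7.5% |
| 22 | 29% | 7.6% |

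The same formula at every K from 12 to 22 stays between 26% and 30%; the maximum is at K = 17 and 19.

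**3. What such a gap does to HbA1c.** Shift = gap × g. A 20-point gap with g = 0.5 moves the estimate by 0.20 × 0.5 = 0.10 point, about 0.3 of the standard error (0.10/0.332). With g = 1.0 the shift is 0.20. The target difference is 1.0.

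**4. Power with one binary term, arms balanced by stratification.** With half the patients bypass and total SD 0.9, the residual SD is √(0.81 − g²/4). One degree of freedom is lost (30 left).

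| g | Residual SD | Power for 1.0 |
|---|---|---|
| 0 | 0.900 | 82.9% |
| 0.3 | 0.887 | 84% |
| 0.5 | 0.865 | 86% |
| 0.8 | 0.806 | 90% |

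The comparator is 83.0% without the term. With the baseline covariate also in the model and SD held at 0.9, the same step is from 82.9% to 82.8%.

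**5. The term without stratification.** The variance of the arm difference is then inflated by (22 × 11/33) divided by the within-stratum sum of squares of the arm indicator. Averaged over unstratified allocations of 33 patients, about half of them bypass, this is 1.035. Power becomes 81.7%, 82.7%, 84.6% and 89.1% for g = 0, 0.3, 0.5 and 0.8. Stratifying and adjusting together is therefore better than adjusting alone.

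**6. Estimates by procedure.** The 95% interval half-width is t × 0.9 × √(1/n1 + 1/n2): ±0.95 HbA1c points at 12 versus 6, and ±1.23 at 8 versus 4. The second is wider than the effect sought.

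**The case against.** The case against acting has force. The cited evidence concerns remission after surgery. This trial enrols patients who already have HbA1c of at least 6.5% and measures six-month change against placebo, and nothing in the documents links procedure to that outcome. Even for remission, the bypass versus sleeve evidence is split, with identical rates at 24 and 36 months in Preliminary Data item 2. Adjustment for baseline may absorb part of any effect, and an imbalance would be visible wherever procedure is tabulated as a patient characteristic. All of this stands. It makes the benefit uncertain, but it does not raise the cost.

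Three stronger readings are tempting, and the documents do not support them.
- A reader might infer that aim 1 promises results by procedure that are never analysed. The full sentence gives breadth across common operations as the reason, and a pooled estimate serves that.
- A reader might infer bias. Random allocation keeps the test valid, and the error rate and confidence interval already allow for chance imbalance.
- A reader might turn the weight-regain means at 24 and 36 months into a procedure-specific shift in the weight comparison. Those means come from an ongoing follow-up whose HbA1c denominators fall from 36 to 23. At 36 months the contrast is 10.3 − 7.6 = 2.7 kg. If 23 per procedure is assumed, its standard error is √(5²/23 + 11²/23) = 2.5 kg. That is too noisy to use.

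**Conclusion.** The point holds as a minor one about precision and chance imbalance. A factor that the protocol itself calls prognostic is used in neither the stated allocation nor the model. The 26% to 30% chance of a 20-point gap assumes unstratified allocation, inferred from the absence of any stated factor, and 12 to 22 bypass patients among 36. The gain in power is nil if surgery type is unrelated to six-month HbA1c change. It reaches about 7 percentage points (83% to 90%) only under an assumed gap of 0.8 HbA1c points. The stated sample size is not in question.

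**What to change.** 1. Reconcile the eligibility text first. Inclusion criterion 1 admits AB, exclusion criterion 2 lists banding, and the Experimental Plan describes a post-gastric-bypass population. The strata cannot be defined until these agree.
2. Stratify the 2:1 allocation, in blocks, by bypass versus non-bypass. A single binary factor is enough at this size.
3. Pre-specify that term in the ANCOVA for HbA1c, weight and body fat, beside the baseline value. If randomization has begun, add the term before unblinding.
4. Estimates by procedure are optional. If shown, give them with 95% intervals as description, without tests.

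The cost is one factor in the randomization list, one model term and one error degree of freedom, with no extra patients. If the term is added without stratification, the cost when surgery type is irrelevant rises to about 1.3 points of power (83.0% to 81.7%), which still leaves the planned 80%.

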Following randomization, subjects will be clinically evaluated at three office visits at 6 weeks, 3 and 6 months by PI and/or the research staff. The primary outcome measures at 6 months post-randomization include HbA1c followed by the change in HbA1c from randomization. Secondary measures include fasting glucose, BMI, change in body weight, blood pressure, lipid profile. Symptomatic hypoglycemia (blood glucose < 70) and drug related side effects (i.e. mycotic genital infections, urinary tract infection) will be monitored with adverse event reporting. Metabolic testing in all subjects at randomization and at 6

months will include a DXA scan for body fat composition and blood for leptin and adiponectin levels.

Rescue glucose lowering therapy will be provided for all subjects with a blood glucose >250 mg/dl. If chronic uncontrolled hyperglycemia (HbA1c $>11\%$) occurs then basal bolus insulin will be implemented. Subjects (20-75 years) who underwent AB, SG or RYGB within the past 15-years will be recruited. Including subjects who underwent surgery within the past 15-years will broaden the subject pool, as additional subjects who initially remitted and were subsequently rediagnosed will be identified. However, we will prioritize subjects who underwent metabolic surgery ≤ 6 years ago and who initially achieved remission status documented by HbA1c of $\leq 6.5\%$ within first year and a subsequent glycated hemoglobin $\geq 7.5\%$ (without any hypoglycemic agents) and less than 11% as upper limit. The rationale to prioritize patients that initially remit is that these patients have demonstrated ability to respond to surgical weight loss and subsequently redeveloped the disease. Whereas those that never achieved initial remission status may not respond to any intervention due to inexorable beta cell failure.

Initial recruitment will be achieved by a general awareness campaign, which will emphasize a study of methods of diabetes management post metabolic surgery. All patients will be pre-screened for inclusion and exclusion criteria by our clinical trial research nurse coordinator and/or research fellow. Evaluation of the inclusion and exclusion criteria, which are listed below, will occur both at the initial screening visit and the baseline visit, prior to randomization.

Statistical Methods

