10. Female patients must agree to use a reliable method of contraception for 6 months

or

duration of intervention.

11. Excluding research-related insulin use, patients taking an anti-diabetic medication, except insulin, are eligible and must

agree to washout for 8 weeks prior to the randomization visit.

Exclusion Criteria:

1. Type 1 diabetes indicated by history of diabetic ketoacidosis and lack of remission in response to bariatric surgery.

2. Other post bariatric procedures (banding, duodenal switch, biliopancreatic diversion)
3. Non-research-related insulin use that is prescribed by the patient's primary care physician or endocrinologist
4. End organ diabetic complications (renal failure, cardiomyopathy, severe neuropathy/foot ulcers)
5. Documented severe or unstable depression/anxiety or eating disorder that would not enable patient to adhere to anti-diabetic treatment.
6. Clinical contraindications to use canagliflozin, i.e., history of bladder cancer, Child-Pugh class C.

In addition to a urine sample, a maximum of 60-cc of blood may be needed at each visit; 30-cc will be stored as a biorepository, for future purposes. The biorepository will be performed at randomization and at the 6 month visit. The research repository collection will be part of the protocol. The identity of the subject will be confidential as the samples will be deidentified. Specimens will be processed and stored in Preventive Research Laboratory at Cleveland Clinic. Access to these specimens will be limited to the designated PRL laboratory personnel and utilized at the discretion of the Principal Investigator.

Schedule of visits summarized:

Visit 1: Consent and Screening Visit: An assessment of clinical status for eligibility will be performed. Review of past medical history and medication usage will be reviewed. Venipuncture for HbA1c and a pregnancy test (females only). Labs for nutritional status

including B12 and 25 hydroxy vitamin D will be performed. Nutritional deficiencies will be addressed per current clinical guidelines for post-bariatric patients.

Visit 2: Baseline Visit: 45 minute visit with diabetes educator for diet/exercise prescription and glucose monitoring based on ADA clinical care guidelines.

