An adverse event is considered unlisted if the nature or severity is not consistent with the applicable product reference safety information. For a medicinal product(s) with a

marketing authorization, the expectedness of an adverse event will be determined by whether or not it is listed in the applicable product information.

III. Special Situations

Safety events of interest for a Janssen medicinal product that require expediting reporting and/or safety evaluation include, but are not limited to:

- Drug exposure during pregnancy (maternal and paternal)
- Overdose of a Janssen medicinal product
- Exposure to a Janssen medicinal product from breastfeeding
- Suspected abuse/misuse of a Janssen medicinal product
- Inadvertent or accidental exposure to a Janssen medicinal product
- Any failure of expected pharmacological action (i.e., lack of effect) of a Janssen medicinal product
- Medication error involving a Janssen medicinal product (with or without patient exposure to the Janssen medicinal product, e.g., name confusion)
- Suspected transmission of any infectious agent via a medicinal
- Unexpected therapeutic or clinical benefit from use of a Janssen medicinal product

These safety events may not meet the definition of an adverse event; however, they are treated in the same manner as adverse events. Special situations should be recorded on the Adverse Event page of the CRF.

Any special situation that meets the criteria of a serious adverse event should be recorded on a Serious Adverse Event Report Form and be reported to Janssen Scientific Affairs **within 24 hours of becoming aware of the event.**

IV. Management of Hyperglycemic Events

A sliding scale will be implemented for the management of hyperglycemia in the placebo or canagliflozin treated groups and during the anti-diabetic medication washout

period if a subject develops random blood sugars >250 mg/dl. Subjects will use the following sliding scale:

Sliding scale with human regular insulin:

0-250: 0 units

251-300- 6 units

301-350- 8 units

351-400- 10 units.

If chronic uncontrolled hyperglycemia occurs (HbA1c > 11%) in the placebo or canagliflozin treated group then basal bolus insulin will be implemented. Basal bolus insulin will be initiated based on body weight calculation 0.5 U/kg/day with 50% of the dose given with long-acting insulins (NPH, glargine) and the remaining dose with meal insulin with rapid acting insulin (Regular, Humalog, Novolog, Apridra etc.).

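### Does the plan need a written rule for 6-month HbA1c measured after protocol rescue insulin?

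*Combined protocol and SAP*

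**What the plan says.** Rescue appears in two places. In Description of the Research Protocol, before Statistical Methods: "Rescue glucose lowering therapy will be provided for all subjects with a blood glucose >250 mg/dl". Section IV, Management of Hyperglycemic Events, makes this a sliding scale of regular insulin in either arm and during washout, and adds: "If chronic uncontrolled hyperglycemia occurs (HbA1c > 11%) in the placebo or canagliflozin treated group then basal bolus insulin will be implemented". Neither place stops study drug or follow-up when rescue starts.

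Statistical Methods defines the primary analysis as a "modified intent to treat analysis which includes all patients receiving at least one dose of the drug they were assigned". The model is an analysis of covariance of change from baseline at 6 months, with group as predictor and baseline as covariate. A per-protocol analysis is described as secondary and optional, "using those demonstrating compliance to their assigned treatment throughout the study". Compliance is not defined further.

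The only text that sets protocol insulin apart from other insulin is in the eligibility criteria. Inclusion criterion 11 opens "Excluding research-related insulin use, patients taking an anti-diabetic medication, except insulin, are eligible and must", and exclusion criterion 3 bars only insulin prescribed outside the research. These are entry rules, not analysis rules.

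**The concern.** Both rescue triggers are glycemic and the primary endpoint is HbA1c, so rescue would tend to fall on patients with high values, and more often on placebo. Only about 11 placebo patients are expected to be evaluable, so one or two rescues can move the placebo mean.

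A reader could see three weaknesses:

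- A 6-month value on insulin might be used as observed, set to missing or replaced, and each choice answers a different question.
- A rescued patient might be kept in the per-protocol set or dropped from it. Dropping would trim the top of the placebo group and pull the estimate toward zero.
- If the choice waited until the data were seen, an analyst could pick the better result. Without rescue counts by arm, nobody outside could judge.

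**Working it through.** **1. The plan's own figure.** Inputs from Sample Size Considerations: 22 vs 11 evaluable, SD 0.9, difference 1.0, two-sided 0.05. Noncentrality = 1.0 / (0.9 × √(1/22 + 1/11)) = 1.0 / (0.9 × 0.369) = 3.01 on 31 degrees of freedom, which gives 83.0% power. At 20 vs 10 it is 79.1%, so 22 vs 11 is the smallest 2:1 design that reaches the stated 80%. Nothing in the rescue question alters this.

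**2. What the text implies for the primary analysis.** Every patient with one dose is in the set, the outcome is 6-month change, and no sentence censors, replaces or excludes a value. The observed 6-month HbA1c is therefore used. This is a treatment-policy comparison: the effect of assignment, with rescue as part of care.

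**3. Size of that default.** With observed values used,

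difference = 1.0 − (placebo rescue share − canagliflozin rescue share) × insulin effect.

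The only insulin figure in the documents is the basal-insulin series in Preliminary Data item 5: 8.1 − 7.3 = 0.8 points. It is uncontrolled and a different regimen, so it only sets the scale. With no canagliflozin rescue and SD held at 0.9:

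- 1 of 11 placebo patients rescued: 1.0 − 0.091 × 0.8 = 0.93, power 77%.
- 2 of 11: 1.0 − 0.182 × 0.8 = 0.85, power 70%.

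With equal rescue in both arms the difference is unchanged. The smaller difference is the true effect of a policy that includes rescue, not bias, and writing the default down would not change it. Holding the SD fixed is also pessimistic, because insulin given to the highest values narrows the spread.

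**4. Keep or remove in the per-protocol set.** This was simulated with the planned covariance model. Assumptions: baseline mean 8.3, SD 1.3, limited to 6.5–11; baseline–change correlation -0.3; correlation 0.8 between 3- and 6-month residuals; one 3-month glycemic threshold for both arms; insulin effect 0.4 or 0.8; true difference -1.0. Power with no rescue is 85%.

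| Placebo rescue | Keep: estimate, power | Remove: estimate, power |
|---|---|---|
| 5% to 30% | -0.99 to -0.85, 85% to 81% | -0.96 to -0.84, 82% to 64% |
| 20% (canagliflozin about 4%) | -0.94 to -0.88, 83% to 80% | -0.86, 69% |

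Part of the loss on removal is simply fewer patients: dropping the same share at random in the 20% case gives 78%.

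**5. How often rescue might occur.** The documents give no rate. For the HbA1c trigger alone, with baseline mean 8.2–8.4 and SD 1.3 assumed, the share of placebo patients above 11% at 3 months is 3.1–3.8% if entry is limited as in Sample Size Considerations ("with HbA1c greater than or equal to 6.5% and less than 11% will be randomly assigned"). It is 4.2–5.4% if there is no upper limit, as inclusion criterion 4 reads for diet-controlled patients ("HbA1c must be greater than or equal to 6.5% at randomization"). Of 11 patients that is 0.031 × 11 = 0.3 up to 0.054 × 11 = 0.6. The two entry statements need reconciling in their own right, but they barely move this figure. The glucose trigger could add rescues at a rate that cannot be derived.

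**6. The responder endpoint (HbA1c below 6.5%).** At 20% placebo rescue, 0.20 × 11 = 2.2 patients. If their values follow the series in item 5 (mean 7.3, SD 0.5), the chance of falling below 6.5 is P(Z < -1.6) = 0.055, and 2.2 × 0.055 = 0.12 of a patient.

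**7. Type I error.** With no true effect and equal rescue, keeping gives 4.8–5.1% and removing 4.8–5.2%. Taking whichever p-value is smaller gives 5.9–8.3%. That figure needs a free choice between the two analyses, and Statistical Methods has already named the modified intent-to-treat analysis as primary.

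**The case for a change.** The strongest case for a change is that the per-protocol question has no stated answer and both readings can be argued. A patient on protocol insulin is following the protocol, yet aim 1 and the Experimental Plan call the treatment monotherapy, so added insulin can be seen as a departure. If rescued patients were dropped, a weaker per-protocol result might be misread as weak efficacy. In an unadjusted t-test with rescue placed on the largest HbA1c rises, in placebo only at 20%, removal gives -0.69 and 50% power, against -0.84 and 75% if they are kept (insulin effect 0.8). Two sentences and a table row would settle it.

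The silence stands, and so does the value of reporting rescue by arm. The size does not. The documented triggers are levels, not rises, and the plan adjusts for baseline; under those conditions removal at 20% gives 69%, not 50%. The order can even reverse: with rescue unrelated to HbA1c change, at 30% placebo and 10% canagliflozin, keeping gives 64% and removing 70%. All of this concerns an analysis that may never be run, under the less natural reading of its criterion, since compliance there refers to the assigned treatment and the protocol itself supplies the insulin.

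**Conclusion.** No change to the plan is needed. This is missing detail that analysts fill sensibly. Followed as written, the plan uses the observed 6-month HbA1c of all dosed patients, and that primary comparison is sound. A sentence saying so would only restate it.

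The open detail is whether protocol insulin alone counts as non-compliance in an optional secondary set. An analyst would normally settle that when defining compliance before unblinding, and would tabulate rescue by arm as routine; Statistical Methods already provides for categorical factors as frequencies and percentages. On the assumptions in the working, the choice moves the estimate by 0.01–0.02 with an insulin effect of 0.8 and by 0.03–0.11 with 0.4, and it lowers the power of that secondary analysis to between 82% and 64% if rescued patients are removed. The sample size, the significance level of the primary test and the responder endpoint (about 0.12 of a patient) are not materially affected.

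The conclusion on the primary analysis rests on the text alone. The sizes rest on assumed rescue rates and insulin effects, because the documents give no rates and only one uncontrolled insulin series.
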